7.1 Treatment

a. Pretreatment Labs:

Blood samples collected for pretreatment laboratory tests must be collected and analyzed no more than 3 days prior to dosing. Albumin, glucose, and electrolytes (Na, K, HC03 or CO2) are required within 3 days prior to dosing to obtain baseline data for future toxicity assessments.

b. Arm 1: **Physician/Patient Choice of Either High Dose Interferon or Ipilimumab**

1. High Dose Interferon

Induction Therapy

Agent	Dose Schedule	Route	Days
Interferon Alfa-2b	20 MU/m ² /d* Weeks 1 - 4	IV over 20 min	1-5 5 days a week

* Dose rounding \pm 10% is allowable per institutional standards.

For the purpose of data reporting, 1 cycle = 6 weeks (4 weeks of HDIFN plus first 2 weeks of IFN maintenance.).

If possible, on the days when patients are required to come in for a clinic visit, Interferon treatment should be administered after all questionnaires, procedures and assessment have been completed.

Interferon doses must be rounded to the nearest 1 million unit. Interferon is given over a 20 minute infusion. Day 1 of each week of induction therapy should be administered at the registering institution. Days 2 – 5 of interferon administration for Weeks 1 - 4 may be administered at an institution other than the registering institution provided that during treatment to-date, the patient has not encountered any life-threatening or unusual toxicities and that the registering physician still retains primary responsibility for the patient's treatment. Documentation concerning all drugs administered, side effects, and tests performed must be forwarded to the registering institution. Home Health Agencies (HHA) may be used to treat patients. The registering institution must document any care given at an outside institution.

Maintenance Therapy

Agent	Dose Schedule	Route	Days
Interferon Alfa-2b	10 MU/m ² /d* Weeks 5 - 52	SC	1, 3, 5 M,W,F

For the purpose of data reporting, Cycle 2 (Weeks 7-12) is 6 weeks, and all subsequent cycles are 12 weeks.

Self-Administration of Subcutaneous Doses

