Interferon doses must be rounded to the nearest 1 million unit. Patients who are deemed competent to self-administer the subcutaneous maintenance doses of Interferon alfa-2b may do so following the first 4 weeks of treatment. Patients must complete compliance documentation ([Section 7.3](#)) for self-administered doses. If patient cannot self-administer, a nurse, or qualified HHA staff may administer the injections. The registering institution must document any care given at an outside institution.

* Dose rounding \pm 10% is allowable per institutional standards.

2. Ipilimumab

Induction Therapy

Agent	Dose Schedule	Route	Days
Ipilimumab	10 mg/kg* Weeks 1-10; weeks total of doses	IV infusion over 90 minutes	1 Q 3 for a four

For the purpose of data reporting, 1 cycle = 6 weeks.

* Dose rounding \pm 10% is allowable per institutional standards.

If possible, on the days when patients are required to come in for a clinic visit, treatment should be administered after all questionnaires, procedures and assessment have been completed.

The final concentration must be between 1-2 mg/mL.

Maintenance Therapy

Agent	Dose Schedule	Route	Days
-------	---------------	-------	------

Ipilimumab 10 mg/kg* IV infusion 1 Weeks
25-145; over 90 Q 12
weeks minutes for 11
doses ending
at 3 years)

For the purpose of data reporting, 1 cycle = 12 weeks.

* Dose rounding \pm 10% is allowable per institutional standards.

If possible, on the days when patients are required to come in for a clinic visit, treatment should be administered after all questionnaires, procedures and assessment have been completed.

The final concentration must be between 1-2 mg/mL.

c. Arm 2: **MK-3475 (Pembrolizumab)**

Agent	Dose	Route	Schedule
MK-3475 weeks (Pembrolizumab)	200 mg	IV over 30 minutes	Day 1, Q 3 for 52 weeks

For the purpose of data reporting, Cycle 1 and Cycle 2 are 6 weeks and all subsequent cycles are 12 weeks.

MK-3475 (pembrolizumab) treatment should be administered after all questionnaires, procedures and assessments have been completed. MK-3475 (pembrolizumab) treatment may be administered up to 3 days before or after the protocol-specified Q 3 weeks due to administrative reasons.

MK-3475 (pembrolizumab) treatment will be administered on an outpatient basis.

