The EQ-5D-3L has two systems. The descriptive system measures three functional domains (mobility, self-care, usual activities) and two symptom domains (pain/discomfort and anxiety/depression). Each domain has three levels (no problems, some problems, extreme problems). A visual analog system (VAS) records self-rated global health between “best imaginable health state” and “worst imaginable health state” and can be used as a quantitative measure of health outcome as judged by individual patients. The three functional and two symptom domains can be summarized categorically, and the VAS global health rating can be summarized quantitatively. The measures can then be combined into a single summary index. Utility scoring will follow the US and European algorithms.

c. **Endpoints:** PRO endpoints are measured by the FACT-BRM, FACIT-D, and EQ-5D-3L. These endpoints are affected by both disease progression and treatment tolerability.

The Trial Outcome Index (TOI) from FACT-BRM is the primary PRO endpoint for this study. The TOI combines four subscales: Physical Well-Being, Functional Well-Being, the BRM Physical Subscale, and the BRM Cognitive/Emotional Subscale. The primary TOI endpoint will be the TOI score at Cycle 3.

Secondary PRO endpoints from the FACT-BRM are the six individual FACT-BRM subscales and the FACT-BRM total score. Secondary PRO endpoints from the FACIT-D are symptom-specific subscale and specific items and the FACIT-D total score. Secondary PRO endpoints from the EQ-5D-3L include the summary index as well as each of the six individual EQ-5D-3L domains.

For PRO endpoints, the baseline score will be accounted for as a covariate in multivariable regression models. The change between the baseline and Cycle 3 scores will also be examined as a sensitivity analysis. In addition, the changes over all time points in the TOI endpoint as well as all of the secondary PRO endpoints will be analyzed using longitudinal data analytic approaches described below.

d. Schedule for PRO data collection:

Table 11.8.1 PRO Data Collection Schedule

Treatment Cycle	Baseline	Cycle 1	Cycle 3	Cycle 5	Cycle 7	Cycle 9	Follow-up	Recurrence
Study Time*	Before first day of treatment	4 weeks	13 weeks	25 weeks	37 weeks	49 weeks	24 and 48 weeks after protocol treatment discontinuation	See below (a, b)

* assuming no treatment delays

a) Once patient has disease recurrence, no subsequent PRO data will be collected.

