For any subscales, trial outcome indexes, or total scores, we also define the minimum completion rate as the number of patients who complete at least one item included in the subscale, TOI, or total score, respectively, in order to assess the extent to which sites successfully administer a form to patients, even if only minimal information on the form is collected and the form cannot be scored according to the missing data rules for the instrument.

The primary reason for not completing any of the PRO assessments for any assessment time point will be collected on the PRO Coversheet, to be filled out by the personnel administering PROs at each site. The reasons will be summarized in table format.

g. **PRO analyses:** Consistent with the design and to aid in clinical interpretation, the analysis of the primary endpoint of the Cycle 3 FACT BRM TOI will be conducted using multivariable linear regression analysis, adjusting for randomization stratification factors and the baseline FACT BRM TOI score as covariates. A window of +/- 2 weeks around the completion of cycle 3 will be allowed for inclusion of the FACT-BRM TOI in the final analysis. We will also conduct longitudinal modeling of the outcome measures over time, to assess whether the longitudinal results are consistent with the primary analysis. Power for the longitudinal analysis will be greater since the addition of all available FACT BRM TOI scores over time will provide more information. For longitudinal modeling, linear mixed models will be used, with random effects for intercepts and slopes and using both compound symmetric and unstructured correlation models. Covariates for longitudinal modeling will include treatment arm, assessment time, their interaction, the baseline score, as well as the randomization stratification variables and the baseline FACT BRM TOI score. Additionally, a treatment by time-squared interaction will be evaluated. These models are nested and so log-likelihood values will be compared using a Chi-squared tests with appropriate degrees of freedom to assess which model provides a best fit to the data. When summarizing results from models with the best fit, coefficients for the intercept, treatment arm, time point, and baseline score will be tabulated, along with 95% confidence intervals and nominal p-values. We will also plot scale and subscale means for groups of patients based on the number of time points that instruments were completed.

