14.4 Data Submission Overview and Timepoints

a. WITHIN 7 DAYS OF REGISTRATION TO STEP 1:

Submit the following:

S1404 Eligibility Checklist, confirmed a patient's eligibility (NOTE: This must be uploaded into Rave® via Source Documentation Baseline Form)

S1404 Onstudy Form

S1404 Medical History Form

Submit slides for PD-L1 evaluation as specified in [Section 15.2](#).

***S1404** Local Pathology Review Form ([Section 18.4](#))

*Radiology reports from all scans performed to assess disease at baseline

*Pathology reports documenting histologic confirmation and complete resection of all disease.

*NOTE: Upload reports via the Source Documentation: Baseline form in Rave®.

b. IF PATIENT WILL NOT BE REGISTERED TO STEP 2 (RANDOMIZATION), SUBMIT WITHIN 7 DAYS OF DECISION NOT TO RANDOMIZE PATIENT:

S1404 Pre-Randomization Off Study Form

NOTE: For patients who do not register to Step 2 (Randomization), no additional follow-up is required other than the items listed in [Sections 14.4a](#) and [14.4b](#).

- c. WITHIN 28 DAYS OF REGISTRATION TO STEP 2 (RANDOMIZATION):
If patient consents to banking, submit specimens as specified in [Section 15.3](#).
- d. WITHIN 14 DAYS OF REGISTRATION TO STEP 2 (RANDOMIZATION):
Submit **S1404** Baseline Laboratory Values Form
Submit to IROC via TRIAD for Image Banking. Images from scans performed to assess disease as specified in [Section 15.6](#).
- e. PATIENTS RANDOMIZED TO ARM 2, MK-3475 (PEMBROLIZUMAB), THEREBY PARTICPATING IN PHARMACOKINETIC (PK) AND ANTI-DRUG ANTIBODY (ADA) TESTING:
Submit specimens as specified in [Section 15.4](#).
- f. WITHIN 14 DAYS AFTER EACH CYCLE OF TREATMENT (CYCLE 1 AND CYCLE 2 = 6 WEEKS EACH; ALL SUBSEQUENT CYCLES = 12 WEEKS):
Submit the following:
S1404 Treatment Form
S1404 Adverse Event Form
S1404 Laboratory Values Form
S1404 Concomitant Medications Form
- g. AFTER RANDOMIZATION, WITHIN 14 DAYS AFTER EACH DISEASE ASSESSMENT, INCLUDING ANNUAL BRAIN IMAGING (SEE STUDY CALENDAR FOR SCHEDULE) UNTIL RECURRENCE (AS DEFINED IN SECTION 10.0) OR 5 YEARS AFTER RANDOMIZATION (WHICHEVER OCCURS FIRST):
Submit the following:
S1404 Disease Assessment Form
Radiology reports from all scans performed to assess disease (uploaded via the Source Documentation: Follow-Up Form in Rave[®])
Submit to IROC via TRIAD for image banking. Images from scans performed to assess disease as specified in [Section 15.6](#).
If patient is no longer on protocol treatment, also submit the Adjuvant Melanoma Follow-up Form

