15.3 Specimens for Banking

Specimens for banking (submitted to the SWOG Specimen Biospecimen Bank – Solid Tissue, Myeloma and Lymphoma Division, Lab #201) (**optional** for patient):

a. Specimen collection kits are not being provided for this submission; sites will use institutional supplies. Please do not use tubes provided by PPD. **Do NOT submit specimens for banking to LabCorp.**

b. With patient's consent, the following specimens must be submitted at the following times:

1. Entire block of paraffin embedded tissue (from primary, lymph node, and metastasis if present) or 10 unstained slides may be submitted if the institution cannot release a pathology paraffin embedded block, **and one H&E (Hematoxylin and Eosin) stained slide** at the following times:
 - Baseline
 - Relapse

Submit tissue according to guidelines provided by SWOG Biospecimen Bank:

<https://www.swog.org/clinical-trials/biospecimen-resources/biospecimen-processing-and-submission-procedures>.

Collect three tubes of whole blood in 10 mL red/black marble top (SST) vacutainer tubes with no anticoagulant. Process whole blood to **serum** according to guidelines provided by SWOG Biospecimen Bank:

<https://www.swog.org/clinical-trials/biospecimen-resources/biospecimen-processing-and-submission-procedures>.

Collect at the following times:

- Baseline (prior to the start of study treatment)
- Start of Cycle 3 (Week 13, if there are no dose delays)
- Start of Cycle 4 (Week 25 if there are no dose delays)
- When patient is removed from protocol therapy for any reason
- Relapse

Collect three tubes of whole blood in 10 mL pink/lavender top vacutainer tubes with EDTA. Process whole blood to **plasma and buffy coat** according to guidelines provided by SWOG Biospecimen Bank:

<https://www.swog.org/clinical-trials/biospecimen-resources/biospecimen-processing-and-submission-procedures>.

Collect at the following times:

- Baseline (prior to the start of study treatment)
- Start of Cycle 3 (Week 13 if there are no dose delays)
- Start of Cycle 4 (Week 25 if there are no dose delays)
- When patient is removed from protocol therapy for any reason
- Relapse

c. If a patient has a treatment delay or interruption due to an adverse event, the blood sample for banking should be drawn even if the patient did not receive study treatment. The goal is to collect the sample as close to the week designated by the protocol.

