15.4 Pharmacokinetic (PK) and Anti Drug Antibody (ADA) testing

NOTE: AS OF 12/11/2017 PK/ADA SAMPLING HAS BEEN DISCONTINUED.

a. Requirements

All patients randomized to the MK-3475 (pembrolizumab arm) will have blood draws for PK and ADA analysis.

b. PK/ADA Sampling for the trial

PK/ADA sampling may be discontinued upon confirmation that results are consistent with the current PK/ADA profile of MK-3475 (pembrolizumab) as determined by the Merck Pharmacokinetics and Pharmacodynamics Drug Metabolism Quantitative Pharmacology and Pharmacometrics group.

c. Specimen Tracking

Specimen submissions must be entered and tracked using the SWOG Online Specimen Tracking System (SpecTrack). See [Section 15.1](#) for instructions.

d. Kit ordering

1. To order initial specimen kits log onto the SWOG Specimen Tracking System (<https://crawb.crab.org/SpecTrack/Logon.aspx>) and click on the link “Specimen kits for **S1404**” at the bottom of the page. When placing this initial order, sites must provide laboratory contact information. For SWOG institutions the fields will be pre-populated based on the current data in the SWOG roster. Please note, the initial order will contain three (3) PK/ADA kits and four (4) PD-L1 kits and may take up to 15 days to be filled by PPD. Once PPD receives site information, a site username will be assigned and faxed to the site on the fax verification form. This username will be used for sites to access the PPD portal to reorder supplies: <http://preclaruslabdata.ppd.com>.

If your site does not receive the fax verification form within 3 days or registration, please call SWOG Data Operations at [name].

2. For subsequent orders only, sites may reorder supplies at <http://preclaruslabdata.ppd.com>. After placing the order, a confirmation email will be sent automatically to the site email address.

e. Frequency

PK and ADA samples will be collected before first infusion Cycle 1 (Week 1), before second infusion Cycle 1 (Week 4), before second infusion Cycle 2 (Week 10), before third infusion Cycle 3 (Week 19), before first infusion Cycle 4 (Week 25), before infusion Cycle 6 (Week 49) and 30 days after discontinuation of study drug (as long as patient has not started new anti-cancer therapy). Samples should be drawn within 24 hours before infusion of MK-3475 (pembrolizumab).

f. Sample collection and preparation procedures

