When a patient is registered on **S1404**, a calendar should be made with dates of upcoming patient-completed questionnaires noted. A copy of this calendar can be given to the patient with the notation that the questionnaires should be completed. You may wish to photocopy the Study Calendar, [Section 9.0](#), and include the patient's name and specific dates. A copy of this should be kept in the patient file.

If a patient refuses or cannot complete the patient questionnaires at one time point, **he or she should be asked to do so at the next scheduled assessment** time. Submit the **S1404** Cover Sheet for Patient-Completed Questionnaires documenting the reason why the questionnaires were not done.

Anyone involved in the collection of quality of life data in SWOG trials should review the training program available on the SWOG website accessible from three

locations. On the SWOG Home Page (prior to member login), in the QUICKLINKS section on the bottom right corner of the page, there is a link to the Patient Reported Outcomes Training. The other two locations that the training is available are after SWOG member login on the CRA Workbench. The Training section and the New CRAs! section both contain access to the Patient Reported Outcomes (PROs) training module. The training program is a narrated set of slides designed to standardize the way quality of life data is collected from patients. Questions regarding the quality of life assessments can be addressed to the SWOG Data Operations Office ([name]).

c. **S1404** Cover Sheet for Patient-Completed Questionnaires

For each time point that the FACT-BRM, EQ-5D-3L, and FACIT-D are administered, the nurse or CRA completes the **S1404** Cover Sheet for Patient-Completed Questionnaires. The Cover Sheet is submitted with the set of patient-completed forms at each scheduled assessment. The Cover Sheet is very important for tracking how and when the patient forms were completed. When a patient-completed form is not administered at a scheduled time point, it is important to know why the assessment did not occur; the form includes potential reasons for a patient not completing a form. See [Section 14.4g](#) for data submission guidelines.

d. QOL Questionnaire Administration Schedule

The FACT-BRM, EQ-5D-3L, and FACIT-D are scheduled to be administered at the following time points:

- Prior to Cycle 1
- Week 4 of the first cycle of treatment
- Prior to Cycles 3, 4, 5 and 6

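### The inclusion window for the primary quality-of-life score is centred on the end of Cycle 3, but the form is scheduled at Week 13, before Cycle 3 begins

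*Combined protocol and SAP*

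**What the plan says.** **Endpoint and schedule.** Section 11.8c defines the primary patient-reported endpoint: "The primary TOI endpoint will be the TOI score at Cycle 3". Table 11.8.1 in Section 11.8d puts the Cycle 3 form at 13 weeks, assuming no delays. Section 15.5d has the questionnaires given "Prior to Cycles 3, 4, 5 and 6". The specimen schedule in Section 15.3 confirms the calendar position of that visit: "Start of Cycle 3 (Week 13, if there are no dose delays".

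**Window.** Section 11.8g then sets the timing rule for the final analysis: "A window of +/- 2 weeks around the completion of cycle 3 will be allowed for inclusion of the FACT-BRM TOI".

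**Cycle lengths.** Section 7.1 says for interferon that "Cycle 2 (Weeks 7-12) is 6 weeks, and all subsequent cycles are 12 weeks" and for pembrolizumab "For the purpose of data reporting, Cycle 1 and Cycle 2 are 6 weeks and all subsequent cycles are 12 weeks". Section 14.4f applies the same lengths to data submission in general: "CYCLE 1 AND CYCLE 2 = 6 WEEKS EACH; ALL SUBSEQUENT CYCLES = 12 WEEKS". Section 15.4e agrees, with pembrolizumab samples taken "before third infusion Cycle 3 (Week 19), before first infusion Cycle 4 (Week 25".

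**A second numbering.** Table 11.8.1 labels Weeks 13, 25, 37 and 49 as Cycles 3, 5, 7 and 9, and dropout patterns 4 to 6 in Section 11.8g refer to nine cycles of therapy. Section 15.5d calls the same visits Cycles 3, 4, 5 and 6.

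**The concern.** The endpoint and the schedule place the primary score at the start of Cycle 3. The inclusion rule is tied to the end of Cycle 3. In this trial those dates are many weeks apart, so a programmer who applied the rule as written would leave out the form that the schedule produces for the primary endpoint.

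The visit matters because it changes what is compared. Ipilimumab induction is four doses, the last at Week 10, with the next dose at Week 25. A Week 13 score is taken about 3 weeks after the last induction dose, and a Week 25 score about 15 weeks after it. Interferon and pembrolizumab are scheduled to continue through both visits. The treatment contrast would therefore mean something different within the control arm, and the visit should not be left to be settled after the scores have been seen.

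**Working it through.** **1. The plan's own figure.** Section 11.8h states 94% power. Inputs: 1,240 eligible patients (Section 11.1), 20% dropout, an effect of 0.25 reduced by 10% to 0.225, and two-sided alpha of 0.05 (Section 11.8h).

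- Patients per arm: 1,240 × 0.8 / 2 = 496.
- z = 0.225 × √(496/2) = 3.54.
- Power = Φ(3.54 − 1.96) = 94.3%.

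The stated figure reproduces. The difficulty is one of timing.

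**2. The clock.** Week w begins w − 1 elapsed weeks after treatment start. The scheduled on-treatment forms at Weeks 4, 13, 25, 37 and 49 therefore fall at 3, 12, 24, 36 and 48 elapsed weeks.

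**3. The window under each reading.**

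| Reading | Window centre (elapsed weeks) | ± 2 weeks | Week 13 form (12) | Scheduled on-treatment forms inside |
|---|---|---|---|---|
| Stated cycles | 6 + 6 + 12 = 24 | 22–26 | 22 − 12 = 10 weeks too early | Week 25 only |
| 6-week cycles (inferred) | 6 + 6 + 6 = 18 | 16–20 | 16 − 12 = 4 weeks too early | none |
| Week 13 visit (proposed) | 12 | 10–14 | inside | Week 13 only |

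**4. Robustness.**

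- If the table's 13 weeks means 13 elapsed weeks, the form is still 22 − 13 = 9 or 16 − 13 = 3 weeks too early.
- If that form is also two weeks late, it falls at 15 elapsed weeks, still before either window opens.
- Treatment delays before Cycle 3 move the form and the cycle end together. Delays within Cycle 3 push the end further away.

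**5. Where the second numbering comes from.** With 6-week cycles, Cycles 3, 5, 7 and 9 would start after 12, 24, 36 and 48 weeks, that is at Weeks 13, 25, 37 and 49. These match Table 11.8.1. No section defines such cycles.

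**6. The nine-cycle criterion.** Section 9.3 gives pembrolizumab as 18 infusions in 5.5 cycles: 2 + 2 + 4 + 4 + 4 = 16 infusions in five cycles, then 2 of the 4 in Cycle 6. Nine cycles arises only if every cycle has two infusions (18/2 = 9). Under the stated definition no pembrolizumab patient can complete nine cycles, so none can meet the therapy condition of patterns 5 and 6. Interferon ends at Week 52, also within Cycle 6, which starts at Week 49 after 6 + 6 + 3 × 12 = 48 weeks.

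**7. Scoring direction.** Section 11.8b says that a higher FACT-BRM score means better quality of life. The description of the cohort plots in Section 11.8g treats higher scores as worse.

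**The case against.** The best defence is that Section 11.8 often uses the language of completion for questionnaires. Evaluability in 11.8e depends on having completed the baseline and Cycle 3 assessments, and 11.8f defines a completion rate in terms of scorable forms. In that vocabulary the window could mean two weeks either side of the Cycle 3 form. The study calendars use the same two-week tolerance around the 24- and 48-week post-treatment questionnaires. This is plausible as intent, and it supports Week 13 as the anchor. It does not rescue the sentence, which refers to completing the cycle and not the form. Nothing elsewhere redefines the phrase.

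The defence is also right that the 6-week numbering is only inferred. The case rests on the stated 6/6/12-week cycles; the 16-to-20-week window is a secondary check.

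A reader might infer three stronger things, none of which the documents support.

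- **That the primary analysis is bound to use Week 25 scores or none.** The endpoint label, Table 11.8.1, Section 15.5d and the evaluability rule all point to the Week 13 form. Only one phrase is out of line.
- **That the 94% power is wrong.** It reproduces.
- **That the losses by Cycle 3 assumed in 11.8h show that the end of Cycle 3 was intended.** That section lists deaths and worsening disease separately and calls the rates conservative. RFS events under Section 10.2 already include deaths, so setting the worsening-disease rate against the RFS model is not like for like. It settles nothing about the visit.

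**Conclusion.** The inconsistency is real and follows from the plan's own dates. As written, the window excludes an on-schedule primary form by 10 weeks under the stated cycle lengths, and by 4 weeks under the inferred ones. This assumes that the completion of Cycle 3 means the end of the treatment cycle, and that patients follow the schedule without delay. The counts of forms refer to on-treatment forms; a post-treatment form from a patient who stopped early could fall inside either window by chance.

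Severity is minor to moderate. The rule governs the primary patient-reported regression, but quality of life is an additional objective (Section 1.3). OS, RFS and the power statement are unaffected. The longitudinal models in 11.8g use all available scores, including Week 13, and are planned as a check on the primary result. The nine-cycle criterion, the cycle labels and the scoring direction are smaller slips that add no weight to the main point.

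**What to change.** In Section 11.8g, replace the anchor with *± 2 weeks around the scheduled Week 13 (start of Cycle 3) assessment*.

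In the same revision of Section 11.8:

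- Define dropout patterns 4 to 6 by the Week 49 (Cycle 6) time point instead of nine cycles.
- Relabel Table 11.8.1 as Cycles 1, 3, 4, 5 and 6 to match Section 15.5d.
- In the cohort-plot sentence of 11.8g, describe lower scores as the worse ones, to match 11.8b.

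The cost is wording only. The Week 13 form is already on the schedule, so no new assessment and no change of sample size is needed. The change should precede the patient-reported analysis. The documents do not say whether that analysis has been run; if it has, the report should state which visit and window were used.
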